Based on a standard deviation estimate of logMAR from a study on ocular albinism patients (Wildsoet C.F., et al: Investigative Ophthalmology and Visual Science: 2000) of 0.23, a minimum of 44 patients is the required recruitment to find a treatment effect of 0.1 logMAR visual acuity with a paired T-test between

changes due to treatment powered at 80%..Anticipated recruitment would be 50 patients total to allow for possible loss-to-follow-up and sufficient accrual.

If a patient discontinues treatment early, the treatment and the reason will be documented, and they will be asked to still report for their data collection appointments. If data is missing from the treatment phase, that patient will be unable to be used in the final analysis. Hence, we plan to recruit extra patients to ensure full data from at least 44 patients.

As previously mentioned, supportive measures are the only treatment modalities available to albinos, if a standard of care group were used it would be therefore, no treatment. The primary outcome is change from baseline, and since albinism is a chronic condition with no change in vision is the well-established natural history no standard of care group will be necessary – all patients enrolled will receive the standard supportive measures in addition to treatment.

Treatment with Carbidopa in combination with Levodopa inhibits decarboxylation of peripheral Levodopa. Carbidopa does not cross the bloodbrain barrier and does not affect the metabolism of Levodopa within the central nervous system. Since its decarboxylase inhibiting activity is limited to extra cerebral tissues, administration of Carbidopa with Levodopa makes more Levodopa available for transport to the brain. Studies show Carbidopa saturates the bodies peripheral Dopa decarboxylase enzyme at approximately 70 to 100 mg (1mg/kg/day) a day. Patients receiving less than this amount of Carbidopa are more likely to experience nausea and vomiting. This is the basis for the higher dose of 4mg/kg/day of Levodopa treatment in this study, at this dose the minimum amount of Levodopa would be available to the retina (a tissue protected by the blood-brain barrier), as the Carbidopa dose of 1mg/kg/day would reach a peripheral enzyme saturation level. This is the basis for the typical starting dose for treatment of Parkinson's disease, but less than half the typical dose for treatment of DRD in children.

Drug dosing:

Levodopa dosages:

Total daily divided	weight lbs	weight kg

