Risks from testing: Patients will undergo a complete ophthalmic exam twice in three months. Children under 7 have this every 6 months and over 7 yearly. Standard, but more invasive testing procedures include: VEP, photography, and OCT. Visual Evoked Potential (VEP) testing is an electrophysiologic recording of brain wave activity similar to EEG recording that takes 10 minutes while subjects watch a computer screen. This test is performed routinely (30 times/wk) on preverbal patient in the clinic and is very well tolerated. Photography and OCT (a form of photography) requires subjects look into the camera while image is captured -- each image is recorded in less than 5 seconds.

Finally, every safety measure will be put into place to limit breaches of confidentiality. Patient confidentiality has been discussed in several areas of this protocol and include, but are not limited to: genotyping results, pregnancy testing of minors, and clinical documentation of visual performance including photographic information.

Statistical:

The primary analysis will be to look at the paired differences of the changes in logMAR due to 3-month treatment for each subject when compared to baseline. Sample size calculations based on finding a 0.1 logMAR difference in visual acuity at 95% confidence, with a standard deviation of .23, shows a minimum sample size of 44 patients needed to find a significant effect with 80% power. Other investigators have used the .2 logMAR vision improvement as marker of utility of vision improvement.⁶

This study will have an intent to treat goal. Anyone that fits the inclusion criteria for the study regardless of baseline logMAR vision or OCA type will be entered in the study. The goal will be to have 50 patients to ensure at least 44 patients in treatment, after any possible dropouts. Stopping criteria for enrollment will be a total recruitment of 50 patients, additionally after 22 patients (half) complete the course of treatment, the data will be analyzed for potential benefit. If significant results are found, the trial will be concluded.

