Data from 19 completed subjects was analyzed. The standard deviation of differences of logMAR (from baseline to on-treatment) has been estimated to be 0.085. Using a more conservative estimate of 0.1, a one-sample t-test with a significance level of 0.05 and power of 80% would be able to detect a difference of 0.053 when 30 subjects are included in the trial. Hence, 30 subjects will enable us to achieve enough power to confidentially test for changes of 0.1 logMAR.

Data collection:

A physician or clinical technician trained in ophthalmology or

ophthalmologic photography will perform clinical data collection during the clinical visit in a private setting. All procedures will be consented to. Results of research testing (genotyping and pregnancy testing) will be kept in a study chart; results of clinical test will be recorded in the UW clinical chart and study chart. Additionally, all the data collection forms will be coded numerically to keep the data separate from any patient identification.

Genotyping (5cc purple top tube)

All tubes will be labeled with a study patient ID number, drawn at the University Station lab. Upon receipt at the central laboratory (Casey Oregon) the lab coordinator will remove the blood from the tubes and transfer it to the centrifuge for DNA extraction. All DNA samples will be held for only 6 months after completion of the study, in the event the testing would need to be validated, and labeled only with study ID number, a number that cannot be identified with a particular individual by anyone outside of the study clinical center at the UW. Casey eye institute will not be using DNA for any additional purposes.

Urine pregnancy testing will be performed anonymously by the UW lab and resulted to the study coordinator within one hour.

Labeling Procedures

Specimen labels will be provided to the clinic by the Study Coordinating Center. Each set of labels will have a unique *5-digit random specimen identification number* that will be pre-printed on the labels. The date the sample was drawn will be completed by the clinical center at the time the specimen is obtained. No other markings will be placed on the specimen or its container that contain personally identifying information.

All study patient records and data with study patient ID numbers and name codes are stored independent from the data, in a locked office at [name]. The clinic coordinator and PI have access to records.

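### The efficacy stop at 22 completers has no adjusted significance level, so the stated 5% error rate becomes about 7.5% to 8.6%

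*Combined protocol and SAP*

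**What the plan says.** The Statistical section sets 50 recruited and at least 44 analysed as the target, then adds a look for efficacy: "after 22 patients (half) complete the course of treatment, the data will be analyzed for potential benefit. If significant results are found", the trial is concluded. The level of significance for that look is not given.

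The levels that do appear belong to the two sample size statements. The main one, in the same section, reads "Sample size calculations based on finding a 0.1 logMAR difference in visual acuity at 95% confidence, with a standard deviation of .23", and "shows a minimum sample size of 44 patients needed to find a significant effect with 80% power". The paragraph that closes the section rests on "a one-sample t-test with a significance level of 0.05 and power of 80" per cent, and supports a total of 30 subjects.

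That closing paragraph also reports that the data had already been examined: "Data from 19 completed subjects was analyzed. The standard deviation of differences of logMAR (from baseline to on-treatment) has been estimated to be 0.085". It does not say whether the mean change was looked at or tested, whether this analysis replaced the one at 22, or whether the 22-patient rule still applies with 30 subjects.

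**The concern.** A trial that tests at 22 patients, stops if the result is significant, and otherwise tests again at the end has two chances of a false positive. If each test is done at 0.05, the overall error rate must exceed 0.05. The 95% confidence and 0.05 level in the document are then not properties of the design it describes.

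This matters more than usual here for three reasons.

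- There is no control group, so the p-value on change from baseline carries the whole inference.
- Under the revised SD of 0.1, the look at 22 has about 99% power for 0.1 logMAR, so it could well decide the trial.
- Trials that stop early on an unadjusted boundary report inflated effects. In simulation, with SD 0.23 and a true change of 0.10, those stopping at 22 show a mean change of about 0.138. With SD 0.1 and a true change of 0.05, they show about 0.063.

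The 19-subject analysis adds a second question. In an open single-arm trial, anyone who computes the SD of the changes holds the changes themselves, so the mean was available as well.

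**Working it through.** **Inputs from the document.** Effect 0.1 logMAR; SD 0.23 (main calculation) or 0.1 (closing paragraph of Statistical); level 0.05; power 80%; interim look at 22; final N of 30, 44 or 50; earlier data analysis at 19. Sidedness is not stated.

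**1. Reproduce the plan's own figures.** For a one-sample t-test, power = P(T > t(1−α/2, n−1)), where T is noncentral t with n−1 degrees of freedom and noncentrality (δ/SD)·√n.

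- δ=0.1, SD=0.23, two-sided 0.05: power is 79.5% at n=43 and 80.5% at n=44. The minimum is 44, as stated. A one-sided test would need only 35.
- n=30, SD=0.1, 80% power: detectable difference 0.0529 two-sided, matching the stated 0.053. One-sided gives 0.0465.

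Both stated figures therefore come from one two-sided test at the full 0.05. Nothing is set aside for a second look.

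**2. Type I error with the look at 22.** Under no effect, the test statistics at n1 and n2 patients have correlation √(n1/n2): √(22/30)=0.856, √(22/44)=0.707, √(22/50)=0.663. The overall error is 1 − P(|Z1|<1.96 and |Z2|<1.96). It was computed from the bivariate normal and checked by simulating 2,000,000 null trials with t-tests on the accumulating data.

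| Looks | Normal theory | t-test simulation |
|---|---|---|
| 22, 30 | 7.4% | 7.5% |
| 22, 44 | 8.3% | 8.4% |
| 22, 50 | 8.5% | 8.6% |

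**3. If the 19-subject data were also tested for effect.** Same method, three looks.

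| Looks | Normal theory | t-test simulation |
|---|---|---|
| 19, 22, 30 | 8.8% | 9.0% |
| 19, 22, 44 | 9.8% | 9.9% |
| 19, 22, 50 | 10.0% | 10.1% |

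If a test at 19 replaced the one at 22, simulation gives 7.9% (final N 30), 8.6% (44) and 8.8% (50).

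**4. Boundaries that restore 5%.** The Lan-DeMets O'Brien-Fleming function, with 0.025 per tail, spends 2 − 2Φ(2.2414/√t) per tail at information fraction t.

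- 22/44, t=0.50: two-sided p<0.0031 at the interim, p<0.0490 at the end.
- 22/30, t=0.73: two-sided p<0.0177 at the interim, p<0.0447 at the end.

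With t-tests at these levels, the simulated overall error is 5.0% and 5.1%.

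**5. Price of the adjustment.** At n=44 and SD 0.23, power of a test at 0.0490 is 80.2%, against 80.5% at 0.05. At n=30 and SD 0.1, the detectable difference at level 0.0447 is 0.054 logMAR, against 0.053. Interim power at 22 for 0.1 logMAR with SD 0.1 falls from 99% to about 98%.

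**The case against.** **The meaning of significant at the interim is not defined, and the look is for benefit.** A strict boundary may have been intended, or only a result in the favourable direction may stop the trial. No boundary is written, so a reader can apply only the stated 0.05. The direction does affect the size. If only benefit stops the trial at 22 and the final test is two-sided, the overall error is 6.2% (N=30), 6.7% (N=44) or 6.8% (N=50). The chance of falsely declaring benefit is then 3.7% to 4.3% against a nominal 2.5%. The inflation is smaller in absolute terms but remains.

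**The 19-subject analysis was for variance only.** This may be true. Only an SD is reported, and a look at the SD alone adds little error. The 9% to 10% figures are therefore conditional. The 7.5% to 8.6% figures do not depend on that analysis.

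**The rule at 22 may be left over from the 44-patient design.** With 30 subjects, 22 is 73% of the data and no longer half. But the sentence stands in the current version and nothing withdraws it. The conflict over the final N is a real ambiguity that must be settled before any boundary is fixed.

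**The study is small and uncontrolled, and a true effect of 0.1 logMAR would usually pass an adjusted look as well.** That is so at SD 0.1. Type I error, however, concerns the case of no effect, and the trial has chosen to state a primary outcome, a level, a power and a stop for benefit.

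**Conclusion.** The concern holds. As written, the design does not have the 5% error rate it states. With two-sided 0.05 at the look at 22 and at the end, the rate is 7.5% to 8.6%, depending on whether the final N is 30, 44 or 50. It is 9.0% to 10.1% if the 19-subject data were also tested for effect, which the document neither says nor excludes.

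These figures rest on two assumptions: that the only stated level is used at every look, and that testing is two-sided with stopping in either direction. Two-sidedness is inferred, because the plan's own 44 and 0.053 reproduce only that way. With one-sided tests at 0.05, two looks give 7.2% to 8.2%. No reading of the rule at an unadjusted 0.05 brings the error back to the stated level. This should be corrected, because it is an operative rule that conflicts with the stated error rate.

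**What to change.** First state which final N governs (30, or 44 analysed from 50 recruited), that testing is two-sided, and whether the 19-subject analysis examined the mean change or the variance only. Then do one of the following.

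**(a) Delete the efficacy stop at 22** and make one final test at 0.05, recording that the 19-subject analysis was for variance only. This costs no power. What is lost is the chance to stop early, which with N=30 saves only 30−22=8 patients.

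**(b) Keep the look with a stated boundary.** With Lan-DeMets O'Brien-Fleming spending, stop at 22 only if p<0.0177 and test at p<0.0447 at the end for N=30, or p<0.0031 and p<0.0490 for N=44. Restate the final significance level to match. A constant level at both looks would also serve (p<0.0331 for 22/30, p<0.0294 for 22/44), but takes more from the final test.

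If the 19-subject data were tested for effect, that analysis counts as a look. Option (a) at 0.05 is then not enough, and the levels in (b) must be recomputed to include it.

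The change is a few sentences in the Statistical section. Under (b), the detectable difference at n=30 moves from 0.053 to 0.054 logMAR, or final-test power at n=44 from 80.5% to 80.2%.
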